7.1.5.1 Post-Study Events

Any SAE that occurs outside of the protocol-specified *safety* follow-up period (~~from the time of booster administration and until the day of next Scheduled Clinic Visit~~) (*after Study Termination Visit or Early Termination Visit whichever is earlier*) and *the investigator* considered to be caused by the study vaccine must be reported to GSK or its designee as ~~spontaneous reporting~~.

7.1.6 Pregnancies

To ensure subjects’ safety, *all* pregnancies must be reported to GSK or delegate *within 2 weeks of site becoming aware of a pregnancy*. If the subject agrees to submit this information, the pregnancy must be followed to determine outcome, including spontaneous or voluntary termination, details of the birth, and the presence or absence of

any birth defects, congenital abnormalities, or maternal and/or newborn complications. This follow-up should occur even if intended duration of safety follow-up for the study has ended.

Pregnancy data must be recorded on a Pregnancy Report CRF (initial report) and Pregnancy Follow-Up CRF (outcome report) and reported to GSK or delegate. Instructions and contact details for submitting the Pregnancy CRFs will be provided to the investigator.

Any pregnancy outcome meeting the definition of SAEs (see section 7.1.4, Serious Adverse Events) reported in subjects who received booster administration needs to be reported within 24 hours of the site becoming aware of the event to GSK or delegate using the VSAE Report Form and be recorded in the CRF(s).

The Pregnancy Form must also be updated for further internal processing.

Any pregnancy outcome meeting the definition of SAEs reported in subjects who have NOT received booster administration need to be reported within 24 hours of the site becoming aware of the event to GSK or delegate using the VSAE Report Form, although such SAEs will not be a part of the Clinical database and do not need to be recorded in the CRF(s).

The Pregnancy Form must also be updated for further internal processing.

8.0 STATISTICAL CONSIDERATIONS

8.1.1.1 Primary Safety Endpoint(s)

For subjects receiving PCEC rabies booster vaccination, SAEs and the associated concomitant medications will be collected starting from the time of booster administration and until the day of next Scheduled Clinic Visit: *completion of safety follow-up period (the day of the next Scheduled Clinic Visit after booster vaccination or on the date of Early Termination Visit, whichever is earlier).*

8.1.1.3 Primary Immunogenicity Endpoint(s)

~~GMCs and GMRs~~ *Geometric Mean Antibody Concentrations* (GMCs) and *Geometric Mean ratio* (GMRs) for subjects receiving the booster dose.

8.1.2.3 Secondary Immunogenicity Endpoint(s)

~~Geometric Mean Antibody Concentrations~~ (GMCs) at Year 3, 4, 5, 6, 7, 8, 9 and 10

8.4.2.1.3 Analysis of Unsolicited Adverse Events

This analysis applies to all ~~serious adverse events~~ **SAEs**

8.4.2.3.2 Analysis Sets

Analyses on PPS will be conducted only if more than 10% of subjects have CSR-reportable **protocol** deviations (by objective).

8.4.2.3.3 Statistical Methods

Kaplan-Meier (**KM**)

Hazard ~~ratios~~ (**HR**)

10.0 DATA MANAGEMENT

10.1 Data Entry and Management

and immunogenicity data will be entered onto ~~case report forms~~ (CRFs) in a timely fashion by the investigator and/or the investigator's dedicated site staff. Data entered onto CRFs are stored on a secure website. The data collected on this secure website are assimilated into an ~~electronic data capture~~ (EDC)

TOC	Table of Content
WHO	World Health Organization

1. BACKGROUND AND RATIONALE

Data on persistence of adequate antibody concentrations (i.e. ≥ 0.5 IU/mL) for up to two years after immunization with *Rabipur* (Rabies, whole virus vaccine) was found in a limited number of pre-exposure prophylaxis (PrEP) studies where the conventional (vaccine administered on days 0, 7, 21 or 28) regimen was administered. There are no data available in literature about persistence of RVNA concentrations following the new, accelerated, one-week (vaccine administered on days 0, 3, 7) PrEP regimen. According to World Health Organization (WHO), booster doses are generally required every 2-5 years and there is no evidence on the best timing for booster administration after 5 years. For this reason, the onset, extent and duration of (sero)protection and the requirement for and timing of booster vaccination following a primary series according to an accelerated or a conventional PrEP Intramuscular (IM) regimen deserves further investigation.

The aim of this study is to evaluate the long-term (up to approx.10 years) persistence and to assess the boostability of immune responses in subjects who received a primary series of accelerated or conventional rabies PrEP IM regimen in V49_23 study.

For further details please refer to section 1.0 of the protocol.

History of changes:

Date	Description	Protocol Version
25 September 2015	First version	Version 1 – 23 February 2015
11 June 2019	Second version/amendment 1: Addition of a mixed model to account for repeated measures within subjects, with inclusion of SAS code. Extension of ± 14 days of the annual Scheduled Clinic Visit window for inclusion of subjects in the Per Protocol Set. Addition of details about subject disposition tables for the purpose of the Interim Analysis. Imputation method of immunogenicity data collected after the administration of a booster dose with application to the long persistence analysis. Modification of the protocol deviations and corresponding PD codes (to fit GSK codes). Details on how to deal with subjects who received a rabies booster dose after conclusion of V49_23 and beginning of V49_23E1 studies. Modification of information regarding the survival analysis: FAS-2 definition, SAS code.	Protocol Amendment 2 – 25 February 2019

Date	Description	Protocol Version
23 Feb 2022	Amendment 2: Inclusion of subjects that received a booster dose between the parent study V49_23 and the current extension study in the FAS-1 booster analysis set. Addition of booster persistence analysis	Protocol Amendment 2 – 25 February 2019

2. OBJECTIVES

Primary Objectives:

Immunogenicity Objectives:

1. To compare the long-term (up to approx.10 years) persistence of antibody responses (i.e. time until antibody concentrations drop below 0.5 IU/mL) in subjects who received a primary series of accelerated or conventional rabies PrEP IM regimen in the parent study V49_23.
2. To evaluate the antibody responses to a booster dose of Purified Chick Embryo Cell-Culture (PCEC) rabies vaccine administered to subjects with Rabies Virus Neutralizing Antibody (RVNA) concentrations < 0.5 IU/mL following a primary series of accelerated or conventional rabies PrEP IM regimen in the parent study V49_23.

Safety Objective:

To evaluate the safety of a booster dose of PCEC rabies vaccine following a primary series of accelerated or conventional rabies PrEP IM regimen in the parent study V49_23.

Secondary Objective:

Immunogenicity Objective:

To evaluate the long-term (up to approx.10 years) immunogenicity in subjects who received a primary series of accelerated or conventional rabies PrEP IM regimen in the parent study V49_23.

3. STUDY DESIGN

This is a phase 3, open-label, non-randomized multicenter, extension study in healthy adults. In the parent study (V49_23) subjects from ≥ 18 years to ≤ 65 years of age were randomized to one of four vaccination groups, three of which for rabies pre-exposure prophylaxis according to conventional (1.0 mL dose of PCEC rabies vaccine administered IM on each of days 1, 8 and 29) regimen, alone or in combination with Japanese Encephalitis (JE) vaccination according to the study group (see [Table 1](#) below) or to a new, one-week, accelerated (1.0 mL dose of PCEC rabies vaccine administered IM on each of days 1, 4 and 8) regimen in combination with JE vaccination.

Table 1 Vaccine Groups in Studies V49_23 and V49_23E1

V49_23 study			V49_23E1 study	
Arm Code (Arm)	Study Vaccine Group N of subjects who received full PrEP and completed the study	Regimen of Primary Vaccine Administration	Study Vaccine Group (from V49_23) Maximum N of subjects who will be invited for enrollment	Regimen of Booster Vaccination
A (Conv-R/JE)	Conventional Rabies + JE vaccination N=158 subjects	Rabies PrEP Days 1, 8 and 29 JE primary series Days 1 and 29	Conv-R/JE N= up to 158 subjects	A single PCEC rabies booster dose (1.0 mL) IM for subjects with RVNA concentrations <0.5IU/mL
B (Acc-R/JE)	Accelerated Rabies + JE vaccination N=209 subjects	Rabies PrEP Days 1, 4 and 8 JE primary series Days 1 and 8	Acc-R/JE N= up to 209 subjects	A single PCEC rabies booster dose (1.0 mL) IM for subjects with RVNA concentrations <0.5IU/mL
C (Conv-R)	Conventional Rabies N=211 subjects	Rabies PrEP Days 1, 8 and 29	Conv-R N= up to 211 subjects	A single PCEC rabies booster dose (1.0 mL) IM for subjects with RVNA concentrations <0.5IU/mL
D (Conv-JE)	Conventional JE N=52 subjects	JE primary series Days 1 and 29	NA	NA

Source: Table 3.1-1 of Protocol Amendment 2 (25 FEB 19)

Subjects who were randomized into one of the 3 rabies vaccination groups (arms A, B and C) of the parent study V49_23, who received the full PrEP rabies regimen and completed V49_23 study following study protocol will be invited to take part to this study.

Subjects who were randomized to the JE conventional group (arm D) in the parent study V49_23 will not be invited to take part to this extension study.

Subjects will receive their booster doses based on their individual antibody concentrations measured over time, i.e., booster will be administered only to those subjects with RVNA concentrations <0.5 IU/mL.

Blood samples will be drawn in all subjects on extension study Day 1 (i.e. approximately three years [Year 3] after completion of rabies primary series in the parent study V49_23) and then at subsequent year intervals from extension study Day 1 (Year 3) onwards (Year 4, 5, 6, 7, 8, 9 and 10 after primary series in the parent study V49_23), to investigate the kinetics of RVNA concentrations.

For further details please refer to section 3.0 of the protocol.

Table 2 Times and Events Table(s) - Scheduled Clinic Visits: For All Subjects

Visit Type		Scheduled Clinic Visit							Final Scheduled Clinic Visit
		Day 1 Year 3	Year 4	Year 5	Year 6	Year 7	Year 8	Year 9	
Study Period		n/a	-28 to +28	Year 10					
Visit Window (Days) *		1	2	3	4	5	6	7	8
Study Event	Protocol references								
Screening and Safety									
Informed Consent ^a	Section 5.1.1	X							
Medical History	Section 5.1.2	X	X	X	X	X	X	X	X
Physical Exam ^d	Section 5.1.2	X	X	X	X	X	X	X	X
Exclusion/Inclusion Criteria	Section 4.0	X	X	X	X	X	X	X	X
Prior and Concomitant Medications	Sections 5.1.2 and 6.5	X							
Assess SAEs and Relevant Medications ^b	Sections 7.1.4, 5.1.2 and 6.5		X	X	X	X	X	X	X
Observe for at Least 15 Minutes Post Blood Draw and Assess AEs (if any)	Section 7.1.3	X	X	X	X	X	X	X	X
Immunogenicity									
Serology Blood Draw	Section 3.5	X	X	X	X	X	X	X	X
Study Completion Procedures									
Study Termination ^c	Section 5.5								X

^a Confirm consent form signed prior to any procedures.^b SAEs and the associated concomitant medications will be collected ONLY from those subjects who will receive booster vaccine during the Ad hoc Clinic Visit, starting from the time of booster administration until completion of safety follow-up period (the day of the next Scheduled Clinic Visit after booster vaccination or on the date of Early Termination Visit, whichever is earlier).^c Subjects who terminate the study early are recommended to complete certain study-related procedures. See Section 5.5 of the Protocol Amendment 2 for further details.^d Physical exams have to be done by practitioners in accordance with their institutional policy. Should the physical assessment reveal any abnormal values or events, which fall under definition of SAE, these must be documented in the CRF Adverse Events Form and reported to sponsor.

*Visit 1 date to be used as reference for calculating next visit date (e.g. V1: 31 JAN 15, V2: 31 JAN 16 ± 28 days, V3: 31 JAN 17 ± 28 days). Additional 14 days will be added to the time window for the inclusion to the PPS (time window will be ± 42 days). It was deemed that additional 14 days would not impact the analysis of immunogenicity persistence.

Table 3 Times and Events Table(s) - Ad hoc and Additional Clinic Visit

Visit Type		Clinic Visit													
		Ad hoc ^a	Additional ^b	Ad hoc ^a	Additional ^b	Ad hoc ^a	Additional ^b								
Study Period	Year 3, between 6 to 9 months after Schedule d Clinic Visit 1	Year 3, 7 days after Ad hoc Clinic Visit 1.1	Year 4, between 6 to 9 months after Schedul ed Clinic Visit 2	Year 4, 7 days after Ad hoc Clinic Visit 2.1	Year 5, between 6 to 9 months after Schedul ed Clinic Visit 3	Year 5, 7 days after Ad hoc Clinic Visit 3.1	Year 6, between 6 to 9 months after Schedul ed Clinic Visit 4	Year 6, 7 days after Ad hoc Clinic Visit 4.1	Year 7, between 6 to 9 months after Schedul ed Clinic Visit 5	Year 7, 7 days after Ad hoc Clinic Visit 5.1	Year 8, between 6 to 9 months after Schedul ed Clinic Visit 6	Year 8, 7 days after Ad hoc Clinic Visit 6.1	Year 9, between 6 to 9 months after Ad hoc Clinic Visit 7.1	Year 9, 7 days after Ad hoc Clinic Visit 7.1	
	n/a	-1 to +1	n/a	-1 to +1											
Visit Window (Days) Visit Number	1.1	1.2	2.1	2.2	3.1	3.2	4.1	4.2	5.1	5.2	6.1	6.2	7.1	7.2	
	Study Event	Protocol references													
Medical History ^c	Section 5.1.2	X		X		X		X		X		X		X	
Physical Exam ^c	Sections 5.1.2 and 5.2	X		X		X		X		X		X		X	
Pregnancy Test ^{c,d}	Sections 3.5 and 5.1.2	X		X		X		X		X		X		X	
Verification of Relevant Exclusion/Inclusion Criteria ^c	Section 4.0	X		X		X		X		X		X		X	
Vaccination ^e	Section 5.2	X		X		X		X		X		X		X	
30 Minutes Post Booster Injection Assessment	Section 5.2.1	X		X		X		X		X		X		X	
Assess SAEs and Relevant Concomitant Medications ^f	Sections 7.1.4, 5.1.2 and 6.5	X	X	X	X	X	X	X	X	X	X	X	X	X	X
Immunogenicity															
Serology Blood Draw	Section 3.5		X		X		X		X		X		X		X
Observe for at Least 15 Minutes Post Blood Draw and Assess AEs (if any)	Section 7.1.3		X		X		X		X		X		X		X

- ^a Ad hoc Clinic Visit (which is planned to occur as soon as the results of the antibody assay will be available and within approximately 6 months from the blood draw taken during a previous "Scheduled Clinic Visit") is only applicable for those subjects with RVNA concentrations <0.5 IU/mL during this extension study. See sections 3.1 and 3.9 of Protocol Amendment 2 for further details.
- ^b Additional Clinic Visit (within approximately 7 days from Ad hoc Clinic Visit) only applicable for subjects who will receive a booster dose of PCEC rabies vaccine during Ad hoc Clinic Visit.
- ^c Procedure to be performed prior to vaccination. Physical exams have to be done by practitioners in accordance with their institutional policy. Should the physical assessment reveal any abnormal values or events, which fall under definition of SAE, these must be documented in the CRF Adverse Events Form and reported to sponsor.
- ^d Only for female subject of childbearing potential who are eligible to receive the booster dose.
- ^e GSK Biologicals' Randomization System on Internet (SBIR) will be used for Treatment allocation.
- ^f SAEs and the associated concomitant medications will be collected starting from the booster administration and until the completion of safety follow-up period (the day of the next Scheduled Clinic Visit after booster vaccination or on the date of Early Termination Visit, whichever is earlier).

4. RANDOMIZATION AND BLINDING

4.1. Method of Group Assignment and Randomization

This is a non-randomized extension study. Subjects previously enrolled in V49_23 study who completed the parent study and are eligible for participation to V49_23E1 study will be identified with a unique Subject ID which is the same they were assigned to during V49_23 study.

For the purpose of the analysis, the arm's name (i.e., Vaccine group) will be the same as in parent study.

Subject will receive a booster dose depending on RVNA concentrations at Scheduled Clinic Visits 1 to 7.

For further details please refer to section 5.1.4 of the Protocol Amendment 2 (25 FEB 19).

4.2. Blinding and Unblinding

Not Applicable.

5. SAMPLE SIZE AND POWER CONSIDERATIONS

No sample size and power analysis was performed for this extension study.

Expected sample size is taken from the number of subjects enrolled in V49_23, assigned to a *Rabipur* vaccine group (i.e., Arms A, B and C), who correctly received the vaccination, completed V49_23 study according to protocol and meet all inclusion criteria and none of the exclusion criteria for this extension study.

6. DETERMINATION OF PROTOCOL DEVIATIONS

6.1. Definition of Protocol Deviations

Major Protocol Deviations (PDs) are defined in GSK WKI_9000059839 as:

- All PD leading to exclusion from analysis population.
- Any protocol deviations which are not leading to exclusion but meet the definition of Major/Critical issue (as per SOP_9000036818).

All major PDs will be evaluated before database lock and classified according to International Conference for Harmonisation of Technical Requirements for Pharmaceuticals for Human Use (ICH) into the following nine categories:

- Fraudulent data (PD code 800)

- Informed consent (PD code 900 & 910)
- Eligibility criteria not met (PD code 2010)
- Assessment or time point completion (PD code 2120 & 2090)
- Study procedures (PD code 2120)
- Excluded medication, vaccine or device (PD code 2040)
- Wrong study treatment/administration/dose (PD code 1070, 1080 & 1090)
- Failure to report safety events per protocol (PD code 2150)
- Study procedures (PD code 2100, 2120 & 2130)

Details of the PD among these categories can be found in the table in the section [7.7](#). Major PDs will lead to exclusion of the subject or part of the subject's data from at least one analysis set. One exception is annual visit out of window; it was decided to include in the PPS also subjects who attended the annual Scheduled Clinic Visit \pm 14 days beyond the allowed time window. It was in fact deemed that additional 14 days would have no impact on the long-term immunogenicity persistence.

The number of subjects in any and by PD category will be summarized by vaccine group, center and overall. Individual subject listings will be provided in an appendix, sorted by subject and by PD category.

Prematurely terminating study participation for reasons such as withdrawal of consent or occurrence of adverse events (including death) is not considered as a PD.

6.2. Determination of Protocol Deviations

Identification of PDs will be done according to the Protocol Deviation Management Plan (PDMP, SOP_9000063106), WKI_130050 and SOP_9000059839.

Periodic Protocol Deviation review will be held as defined in the PDMP. Prior to these periodic meetings all PD trackers for manually identified protocol deviations will be merged with those identified programmatically.

After the review consolidated tracker will be uploaded to SAS Drug Development (SDD) as reference for next review meeting.

7. ANALYSIS SETS

Analysis sets are defined for each study objective and type of analysis.

7.1. All Enrolled Set

All screened subjects who provide informed consent and provide demographic and/or other baseline screening measurements.

Demography and baseline characteristics tables as well as subject listings will be produced on the All Enrolled Set.

7.2. Exposed to Booster dose

All subjects who receive at least one dose of booster during trial.

7.3. Full Analysis Set (FAS), Immunogenicity

FAS-1: Booster immunogenicity analysis

All subjects in the Enrolled Set who receive at least one booster dose during the trial (because RVNA value below 0.5 IU/mL at scheduled visit) or before entering the trial (e.g. travellers to endemic areas or veterinarians who got the booster regardless of the RVNA value) and provide immunogenicity data.

FAS-2: Long term immunogenicity analysis

All subjects in the Enrolled Set who provide immunogenicity data.

Note: In the long-term immunogenicity analysis, when a subject receives a rabies vaccine booster dose (before or during the study) because RVNA value is below 0.5 IU/mL, subsequent RVNA values after the booster dose will be set to half of the detection level (i.e. 0.1 IU/mL) until study end even if the subject withdraws earlier than last study visit (see last part of section [8.2](#) for a detailed explanation).

In case a subject receives a booster dose before or after entering the study (e.g. travellers to endemic areas, veterinarians) but the last known RVNA value was above 0.5 IU/mL, then he/she will be excluded from the long term immunogenicity analysis set (i.e. FAS-2 and PPS). This is justified by the fact that including actual values as recorded after the booster dose would inflate the immunogenicity persistence; on the other hand, it would be inappropriate to apply the same rule used for subjects receiving a booster dose when RVNA value is less than 0.5 IU/mL as this is not the case.

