7.7. Overview of Analysis Sets by PD Code

Table 4 Safety Sets: applicable to Exposed to Booster dose subjects only

PD code	PD Description and Exclusion Reasons	Study Objective/Period	Exposed Set	Safety Set	
			Exclusion code	EXPFL	SAFFL
1070	incomplete treatment course. Booster was not administered although subject had RVNA concentration of <0.5 IU/mL	All Study		EXC	EXC
2150	Subject did not provide any post-booster safety data	Approx. 6 months after booster exposure*			EXC

* For further details refer to study protocol

EXC = excluded from this analysis set.

Table 5 Immunogenicity Sets

PD code	PD Description and Exclusion Reasons	All ENROLLED	FAS 1	FAS 2	PPS 1	PPS 2
		Exclusion code	ENRFL	FAS10FL	FAS20FL	PPS10FL
800	Fraudulent data		EXC	EXC	EXC	EXC
900	Signed informed consent not available on site				EXC	EXC
900	Wrong informed consent version signed				EXC	EXC
900	Informed consent not signed and/or dated by subject				EXC	EXC
900	Informed consent not signed and/or dated by appropriate site staff.				EXC	EXC
900	Informed consent not signed prior to any study procedure (examples: a, b, c)				EXC	EXC
900	Other informed consent deviations				EXC	EXC
910	Partially or inappropriately signed ICF				EXC	EXC
1070	Booster was administered although subject had RVNA concentration ≥ 0.5 IU/mL			EXC	EXC	EXC
1070	Route of administration is wrong or unknown				EXC	
1070	Administration of booster vaccine at wrong visit				EXC	
1070	Commercial vaccine used in place of study vaccine (but same vaccine)				EXC	
1070	Study treatment administered while contraindication				EXC	
1070	Study treatment not prepared as per protocol (e.g. reconstitution)				EXC	
1070	Incorrect Volume was given				EXC	
1080	Use of study treatment impacted by a temperature excursion which was not reported or approved, or which was disapproved for further use.				EXC	
1090	Expired study treatment administered				EXC	
2010	Eligibility Criteria Not Met				EXC	EXC
2040	Prohibited concomitant medication (interval + type)				EXC	EXC
2040	Prohibited concomitant vaccination (interval + type)				EXC	EXC

PD code	PD Description and Exclusion Reasons	All ENROLLED	FAS 1	FAS 2	PPS 1	PPS 2
		ENRFL	FAS10FL	FAS20FL	PPS10FL	PPS20FL
2040	Other excluded medication, vaccine or device deviation				EXC	EXC
2090	Blood draw after booster dose outside 7 (+/- 1 day) day interval				EXC	EXC

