8.5. Immunogenicity Subsets

Descriptive statistics of RVNA persistence following a booster dose administration will be carried out at the end of the study. This will include subjects in the FAS-1 aggregated by year of booster receipt: i.e. subset FAS-1 year 3, FAS-1 year 4 and so forth.

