11.2. Primary Objectives Analysis

Primary Immunogenicity Objectives:

1. To compare the long-term (up to approx.10 years) persistence of antibody responses (i.e. time until antibody concentrations drop below 0.5 IU/mL) in subjects who received a primary series of accelerated or conventional rabies PrEP intramuscular (IM) regimen in the parent study V49_23.
2. To evaluate the antibody responses to a booster dose of Purified Chick Embryo Cell-Culture (PCEC) rabies vaccine administered to subjects with Rabies Virus Neutralizing Antibody (RVNA) concentrations < 0.5 IU/mL following a primary series of accelerated or conventional rabies PrEP IM regimen in the parent study V49_23.

Primary hypotheses:

There is no null hypothesis associated to primary objectives.

Time to first RVNA concentrations < 0.5 IU/mL

Cox proportional hazards regression model

Since, already at the end of the parent study (Day 366, study V49_23) it was observed a difference in the persistence of adequate RVNA concentrations between subjects who have received the accelerated PrEP schedule and those who received the conventional rabies vaccines schedule, the HR from the Cox proportional hazards regression model will be used as a treatment effect measure for time to event endpoints.

Statistical model:

An adjusted proportional hazards regression Cox model will be used:

$$h(t) = h_0(t) \cdot \exp(\beta_1 x_1 + \beta_2 x_2)$$

where:

t represents the survival time

$h(t)$ is the hazard function as determined by the covariates treatment and center

$h_0(t)$ is the baseline hazard function at time t

X_1 represents treatment

X_2 represents center

β_1 and β_2 are the unknown parameters for treatment and center, to be estimated.

The HR is a multiplicative constant $\exp(\beta_1)$ comparing the hazard function in the accelerated schedule group relative to the hazard function in the conventional schedule group.

The HR will be derived from the Cox proportional hazards model using SAS PROC PHREG (with TIES=EXACT).

HR point estimate(s) will be based on partial maximum likelihood function, and Wald-test based two-sided 95% confidence intervals will be requested by the RISKLIMITS option.

The following SAS code will be applied:

```
PROC PHREG data=<dataset>;
  class arm center;
  MODEL survtime*status(0)=ARM center/ TIES=EXACT RISKLIMITS;
  RUN;
```

survtime represents variable containing event/censoring times.

status represents censoring variable (0=censored, 1=event).

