Estimation of survival functions

The term “survival function” $S(t)$ is used here in its general meaning as probability of experiencing a specific event at time t or later. The event of interest is the time when **RVNA concentrations < 0.5 IU/mL**.

A graphical estimate of the survival function separately for each vaccine schedule group will be obtained by the KM product - limit method as implemented in SAS PROC LIFETEST.

Together with the KM curve, the 95% CIs, will be estimated and displayed per each vaccination regimen. Standard errors of the KM estimates will be based on the Greenwood’s method; 25th and 75th percentile and median survival will be provided if estimable.

Data will include observations at 7 days after primary vaccine schedule and at 3, 5 and 12 months from the parent study (V49_23) and the year observations from this study.

```
PROC LIFETEST data=<dataset> plots=(survival(atrisk) logsurv);  
TIME survtime*Status(0);  
STRATA arm;  
RUN;
```

Immune response to booster dose

Geometric Mean Concentration and Geometric Mean Ratios (GMR)

For subjects receiving a booster dose, analysis of boostability will be conducted 7 days and 6 months after administration of the booster dose by providing GMRs and associated 95% CIs, considering the antibody value before the booster visit (i.e., 6 months before following the blood drawn during previous Scheduled Clinic Visit) as baseline (denominator) and the antibody concentration at 7 days and at 6 months after booster as the numerator.

Independently of the time (i.e., visit) a subject receives a booster dose of PCEC vaccine, RVNA concentration as detected from the blood drawn during previous scheduled clinic visit (approximately six months before the booster administration) will be considered baseline value and summarized by the mean of GMC, with associated 95% CIs, median, minimal and maximal values for each vaccine schedule group. In the same table the 7 days and 6 months post booster dose response and geometric mean ratio will be described. ***Percentage of subjects with RVNA concentrations ≥ 0.5 IU/mL***

No inferential model is defined for the binomial variable (i.e., subject with RVNA concentrations ≥ 0.5 IU/mL). Percentages of subjects at 7 days and at 6 months (i.e., at subsequent Scheduled Clinical Visit) after the booster dose will be presented together with 95% CIs (Clopper, 1934) by primary vaccine schedule (arm).

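### FAS-1, the set named for the primary booster analysis, is wider than objective 2, and SAP 7.3, 7.7 and 8.8 disagree on who belongs in that analysis

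*SAP*

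**What the plan says.** Objective 2 (SAP 2, repeated in 11.2) is about a PCEC booster "administered to subjects with Rabies Virus Neutralizing Antibody (RVNA) concentrations < 0.5 IU/mL". Protocol 8.4.2.3.2 lists FAS-1 as the booster immunogenicity set for the primary objectives.

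SAP 7.3 builds FAS-1 from two groups. The first is subjects boosted in the trial because a scheduled RVNA value was below 0.5 IU/mL. The second is subjects boosted "or before entering the trial (e.g. travellers to endemic areas or veterinarians who got the booster regardless of the RVNA value". The SAP history of changes shows that the second group was added deliberately in February 2022, together with a booster-persistence analysis; the protocol version stayed the same. SAP 8.8 recognises that a booster may be the study vaccine or a different rabies vaccine, and SAP 10.1 tabulates boosters received before entry, so such subjects are expected.

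Table 5 (SAP 7.7) has a PD 1070 row that begins "Booster was administered although subject had RVNA concentration" and continues with 0.5 IU/mL or more. It excludes these subjects from FAS-2, PPS-1 and PPS-2; the FAS-1 cell is blank.

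For the results, SAP 11.2 states: "Percentages of subjects at 7 days and at 6 months (i.e., at subsequent Scheduled Clinical Visit) after the booster dose will be presented". SAP 8.5 adds descriptive persistence after the booster: "This will include subjects in the FAS-1 aggregated by year of booster receipt". SAP 11.4 adds a further evaluation of booster persistence from annual visits and names neither a set nor a split. SAP 8.8, however, places subjects for the boostability GMC and percentages in the Exposed to Booster set, which SAP 7.2 restricts to boosters given during the trial.

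**The concern.** The objective asks what a study booster does in people who have lost an adequate titre. A traveller boosted outside the trial, perhaps with another product and perhaps with a titre well above 0.5 IU/mL, does not answer that question. The percentage at later Scheduled Visits is part of a primary endpoint (protocol 8.1.1.3), and protocol 8.3.4 assigns that endpoint to any enrolled subject with data after a booster. Mixing the two kinds of subject would give an estimate that belongs to neither population, at an interval that the label does not describe.

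SAP 7.3 already sees the difficulty on the other side. It removes subjects boosted with a last value above 0.5 from the long-term set FAS-2, because their later values would overstate persistence. FAS-1 has no matching protection.

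**Working it through.** There is no planned figure to reproduce. SAP 5 says "No sample size and power analysis was performed for this extension study", and the 578 subjects to be invited (158 + 209 + 211 = 578) are not a count of boosted subjects. The check is therefore about who can enter which result.

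**Step 1: populations named for the booster analysis**

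| Place | Population |
|---|---|
| Objective 2 (SAP 2, 11.2) | boosted at RVNA <0.5 |
| Protocol 8.4.2.3.2 | FAS-1 |
| SAP 7.3 (FAS-1) | in-trial after a scheduled value <0.5, or before entry at any value |
| SAP 7.7, Table 5, PD 1070 | boosters at ≥0.5 not excluded from FAS-1 |
| SAP 8.8 with 7.2 | all boosted in the trial, none boosted before it |

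**Step 2: what a pre-entry boosted subject can contribute**

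- Day-7 percentage, GMC and GMR: nothing. Protocol 3.5 draws that sample only after an in-trial Ad hoc Visit, and SAP 8.2 leaves missing values out.
- GMR at the later time point: nothing. It is a within-subject ratio (SAP 8.8), and its denominator is the previous Scheduled Visit (SAP 11.2). Scheduled Visits start on extension Day 1, so no such value precedes the booster.
- Percentage and GMC at the next Scheduled Visit: the Visit 1 value, if FAS-1 governs; nothing, if 8.8 governs.
- Booster persistence (SAP 8.5, 11.4): annual values from Visit 1. The strata named in 8.5 begin at year 3, with none for earlier boosters.

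A subject boosted in the trial at ≥0.5 IU/mL would have both a baseline and a day-7 sample, and so could enter every result if the blank cell in Table 5 governs.

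**Step 3: interval since booster**

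- In-trial: boosted 6 to 9 months after a Scheduled Visit, with the next visit at 12 months. 12 − 9 = 3 and 12 − 6 = 6, so 3 to 6 months before allowing for visit windows.
- Pre-entry: any time between the end of the parent study and Visit 1. With the planned days in SAP 8.8, 3 × 365 − 365 = 730 days, or up to about 24 months.
- The label in SAP 11.2 is 6 months.

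**Step 4: illustrative size**

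Let w be the share of non-target subjects, p the percentage ≥0.5 IU/mL in the target population and q that in the others. None of these is given. The shift is w × (q − p); with q = 1 it is at most w × (1 − p), in percentage points:

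| w | p = 0.70 | p = 0.80 | p = 0.90 | p = 0.95 |
|---|---|---|---|---|
| 5% | 1.5 | 1.0 | 0.5 | 0.25 |
| 10% | 3.0 | 2.0 | 1.0 | 0.5 |
| 20% | 6.0 | 4.0 | 2.0 | 1.0 |

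With assumed counts, 80/100 = 80.0% (Clopper-Pearson 95% CI 70.8 to 87.3) becomes 90/110 = 81.8% (73.3 to 88.5) after adding ten subjects, all at or above 0.5.

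For the next-visit GMC, an assumed mean difference d in log10 units changes the pooled value by a factor 10^(w × d): 10^(0.05 × 0.3) = 1.04, 10^(0.10 × 0.5) = 1.12 and 10^(0.20 × 0.5) = 1.26. The direction is open: a higher titre at the booster would raise the pooled value and a longer interval would lower it.

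For the GMR only the Table 5 group matters. If its GMR is a fraction r of the target GMR, the pooled GMR is multiplied by r^w. At w = 10%, r = 0.1, 0.25 and 0.5 give 0.794, 0.871 and 0.933.

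**The case against.** The strongest reply is that SAP 8.8 already confines the boostability GMC and percentages to in-trial recipients, with time points before the booster, at 7 days and at 6 to 9 months. A Visit 1 sample after an outside booster need not fit any of these. The pre-entry group was added in the same amendment as the persistence analysis, which was probably its purpose. There, 8.5 splits by year of booster, so on a plain reading pre-entry boosters are not pooled with later ones, and the evaluation in 11.4 is listed under other analyses. Nothing is tested either: "There is no null hypothesis associated to primary objectives".

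Much of this stands, and it rules out two stronger readings. A reader might infer that pre-entry boosters distort the day-7 response and the GMR; Step 2 shows that they cannot. A reader might also infer that the SAP decides to keep in-trial boosters given at ≥0.5 in FAS-1. It does not: 7.3 itself limits in-trial boosters to values below 0.5, so the blank cell is a contradiction to be resolved. Such boosters would in any case be deviations.

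The reply does not dispose of the point. Section 8.8 conflicts with the protocol's naming of FAS-1 and does not govern persistence. Section 8.5 provides no stratum for pre-entry boosters, and 11.4 provides no split.

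The per-protocol analysis is only a partial safeguard. It is run only if it differs from the FAS by more than 10%, and no row of Table 5 expressly removes pre-entry boosters. Receipt of non-study rabies vaccine after the parent study is an exclusion at Scheduled Visits (protocol 4.2). If it were coded as PD 2010 or 2040, those subjects would leave PPS-1, and a share above 10% would trigger the analysis. That coding is not stated.

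**Conclusion.** FAS-1 is wider than objective 2, and the documents do not settle which set produces the primary booster results. If FAS-1 governs, the percentage and GMC at the next Scheduled Visit and the booster-persistence results can include subjects outside the objective, at intervals of up to about 24 months against 3 to 6 months for in-trial boosters. If 8.8 governs, the boostability GMC and percentages are free of pre-entry boosters, but FAS-1 then loses its role in the analysis for which the protocol names it. The day-7 results and the GMR are at risk only from in-trial boosters given at ≥0.5, and only if Table 5 prevails over 7.3.

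The size cannot be derived, because the number of affected subjects and their titres are not given. Under the assumed shares of 5% to 20%, the percentage would be overstated by at most 0.25 to 6 points, and the GMC would move by a factor of 1.04 to 1.26 for differences of 0.3 to 0.5 log10. These figures are illustrations. The point deserves correction because it leaves the population of a primary estimate undefined; no test or success criterion depends on it.

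**What to change.** Define one set for objective 2: enrolled subjects who received the study booster in the trial after a scheduled RVNA below 0.5 IU/mL and who have post-booster data. Use that set in SAP 7.3, 8.8 and 11.2. In Table 5, add EXC under FAS-1 in the PD 1070 row for boosters given at RVNA ≥0.5.

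Report subjects boosted before entry in a separate descriptive table by actual time since booster, and keep them out of the pooled persistence evaluation in 11.4.

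The cost is a change of SAP wording, one extra table and slightly fewer subjects in the booster set. No new data collection is needed for the main set.
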